9.4 Confidentiality

Patient records will be kept in a secure location at Stanford University Medical Center accessible only to research authorized personnel. Patient identity will be kept as confidential as possible as required by law. The patient will not be identified by name, social security number, address, telephone number, or any other personal direct identifier. Study patients will be assigned an identification code. Information about the code will be kept in a secure location and access limited to research study personnel. The results of this study may be presented at scientific or medical meetings or published in scientific journals, however patient identity will not be disclosed. Personal data included in the investigators' database will be maintained in compliance with all applicable laws and regulations.

10. STATISTICAL CONSIDERATIONS

10.1 Statistical Analysis

The sample size determination for the clinical trial will follow a single arm Simon 2-stage trial principle. The null hypothesis that the true response is $p_u = 0.40$ will be tested against a one-sided alternative ($p_d = 0.7$). In the first stage, $n_1 = 11$ patients will be accrued. If there are $r = 7$ or fewer responses in these $n_1 = 11$ patients, the study will be stopped. Otherwise, $n - n_1 = 9$ additional patients will be accrued for a total of $n = 20$. The null hypothesis will be rejected if $r + 1 = 11$ or more responses are observed in $n = 20$ patients. This design yields a type I error rate of $\alpha = 0.10$ and power of $1 - \beta = 0.90$ when the true response rate is $p_d = 0.70$.

We plan to use a dose of 80 cGy of TBI on Day -1 of HCT. It is fully expected that this low-dose will be safe and not provoke or increase the risk of GVHD or other complications. Patients will be evaluated for toxicities, defined as new Grade 3 to 4 toxicities, according to the Common Terminology Criteria for Adverse Events (CTCAE) v.5 and Grade 3 to 4 GVHD (Appendix A) during the 90 days following HCT.

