2.7 Study Rationale

The persistence of mixed hematopoietic cell chimerism is associated with a significantly high risk of disease relapse after allogeneic HCT [13, 28-30]. Once the patient's disease has relapsed after allogeneic HCT, the likelihood for long-term survival is poor. Therefore, a strategy that can help promote conversion of mixed to complete hematopoietic cell chimerism prior to disease relapse, and does not promote significant GVHD has the potential to help improve the outcomes of allograft recipients by reducing the risk of disease relapse. The goal of the current proposed trial will be to determine if the addition of very low-dose TBI to standard TLI-ATG conditioning therapy will increase the proportion of patients with FDC at Day 28 post-transplant, without reducing tolerability or increasing transplant morbidity. We **hypothesize** that the addition of very low-dose TBI at 80 cGy to TLI-ATG will result in at least a 30% increase in the proportion of patients with FDC in the CD3 subset at Day 28 post-HCT. This study will follow a single-arm Simon 2-stage trial principle. In Simon stage 1, we will enroll 11 patients, and if 5 or fewer patients respond, defined as $\geq 95\%$ donor chimerism in the CD3 compartment at Day 28, we will stop for futility. If 6 or more respond in Simon stage 1, then in stage 2 we will continue to enroll a full sample of 20 patients and declare success if a total of 11 or more patients respond. The primary endpoint will be the determination of the rate of conversion from mixed to complete donor chimerism. Secondary endpoints will include the risk of acute and chronic GVHD, freedom from disease progression, event-free and overall survival, and the relapse rate. The goal is to improve the rate of attaining complete chimerism without increasing the risk of GVHD. If following the Simon 2-stage trial the results are encouraging, we will expand our experience to a broader trial to determine if the TLI/ATG/low-dose TBI is associated with significantly lower rates of disease relapse.

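### Stage 1 futility cut-off is 5 of 11 in Section 2.7 but 7 of 11 in Section 10.1; the Section 10.1 rule has 57% power, not the stated 90%

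*Combined protocol and SAP*

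**What the plan says.** The combined protocol and SAP describes the Simon two-stage design twice.

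- **Section 2.7 (Study Rationale):** "In Simon stage 1, we will enroll 11 patients, and if 5 or fewer patients respond", the trial stops for futility. It then gives the complementary rule: "If 6 or more respond in Simon stage 1, then in stage 2 we will continue to enroll a full sample of 20 patients". Success is 11 or more responders in total.
- **Section 10.1 (Statistical Analysis):** "If there are $r = 7$ or fewer responses in these $n_1 = 11$ patients, the study will be stopped". Otherwise 9 more patients are added, for a total of 20. The final rule is "The null hypothesis will be rejected if $r + 1 = 11$ or more responses are observed in $n = 20$ patients".

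Section 10.1 gives a null response rate of 0.40, a one-sided alternative of 0.70, a type I error of 0.10 and power of 0.90. It attributes these error rates to the design it has just described.

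**The concern.** The two sections share the Stage 1 size, the total size and the final success threshold. They differ only in the number of Stage 1 responders that ends the trial. With 6 or 7 responders among the first 11, Section 10.1 stops and Section 2.7 continues. Nothing in the document says which section governs.

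A cut-off of 7 of 11 is also hard to square with the design's target. The expected Stage 1 count at a 70% response rate is 11 × 0.70 = 7.7, so a regimen that meets the target would often fall at or below 7. Power of 0.90 is then implausible.

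At stake are whether the Stage 1 decision followed the protocol, and which error rates may be quoted with the result. Section 10.1 also uses one symbol, r, for two quantities: 7 at Stage 1 and, by implication, 10 at the end. This is a notation fault, since both thresholds are spelled out, but it makes the slip harder to spot.

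**Working it through.** **Inputs** (Section 10.1 unless noted)

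- Null rate 0.40, alternative 0.70, one-sided
- Stage 1: n1 = 11; Stage 2: 9 more; total n = 20
- Success: 11 or more of 20 (Section 2.7 agrees)
- Stage 1 cut-off r1 (stop at r1 or fewer): 7 in Section 10.1, 5 in Section 2.7
- Stated type I error 0.10, power 0.90

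**Formulas**

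Let X1 ~ Binomial(11, p) and X2 ~ Binomial(9, p), independent.

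- P(stop at Stage 1) = P(X1 ≤ r1)
- P(declare success) = Σ over x = r1+1 to 11 of P(X1 = x) × P(X2 ≥ 11 − x)

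Type I error is the second quantity at p = 0.40; power is the same quantity at p = 0.70.

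**Terms at p = 0.70**

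| x | P(X1 = x) | P(X2 ≥ 11 − x) | Product |
|---|---|---|---|
| 6 | 0.1321 | 0.9012 | 0.1190 |
| 7 | 0.2201 | 0.9747 | 0.2146 |
| 8 | 0.2568 | 0.9957 | 0.2557 |
| 9 | 0.1998 | 0.9996 | 0.1997 |
| 10 | 0.0932 | 1.0000 | 0.0932 |
| 11 | 0.0198 | 1.0000 | 0.0198 |

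- Cut-off 5 sums x = 6 to 11: power 0.902. This reproduces the stated 0.90.
- Cut-off 7 sums x = 8 to 11: 0.2557 + 0.1997 + 0.0932 + 0.0198 = 0.568.

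The difference is the x = 6 and x = 7 rows: 0.1190 + 0.2146 = 0.334.

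**Results**

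| Stage 1 rule | Type I error | Power | Stage 1 stop, p = 0.40 | Stage 1 stop, p = 0.70 |
|---|---|---|---|---|
| Stop at ≤ 5 (Section 2.7) | 0.0990 | 0.9020 | 0.7535 | 0.0782 |
| Stop at ≤ 7 (Section 10.1) | 0.0235 | 0.5684 | 0.9707 | 0.4304 |

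**Could another reading rescue the 7?**

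- Changing the final threshold cannot. At p = 0.70 the chance of passing Stage 1 is 1 − 0.4304 = 0.5696, and power cannot exceed that.
- Reading the rule as fewer than 7 (stop at ≤ 6) gives type I error 0.0597 and power 0.7829.
- Ignoring the interim look (11 or more of 20, single stage) gives 0.1275 and 0.9520, so the type I error exceeds 0.10.
- With n1 = 11 and n = 20, Stage 1 cut-offs of 2 to 8 were crossed with success thresholds of 10 to 13. Only cut-off 5 with success at 11 meets both type I error ≤ 0.10 and power ≥ 0.90.
- A search over designs with total n from 10 to 30 under the same two constraints returns n1 = 11, r1 = 5, n = 20, success at 11 as the Simon optimal design. Its expected sample size under the null is 11 + (1 − 0.7535) × 9 = 13.2.

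**How often the sections conflict**

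They give different instructions when X1 is 6 or 7.

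- p = 0.70: 0.1321 + 0.2201 = 0.352
- p = 0.40: 0.1472 + 0.0701 = 0.217

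**The case against.** The best defense is that this is one mistyped digit in a soundly powered trial. Every other element of Section 10.1 fits the Simon optimal design with a cut-off of 5, and Section 2.7 states that design in full, including the continuation rule. Accrual is already closed (Section 6), so the Stage 1 decision is past and nobody will now stop the trial because of the 7. A positive result is not inflated by either rule: the type I error is at most 0.10 under both, and the final threshold is the same. If Stage 1 gave 5 or fewer responders, or 8 or more, the sections agree and the discrepancy had no effect.

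Most of this stands. The typing-error reading is the likely one, and the 43% early-stop figure shows what Section 10.1 would do if followed; it is not a live risk.

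It does not remove the need for a correction. The document gives neither the Stage 1 count nor the cut-off used, and 6 or 7 responders was a likely outcome. If that occurred and the trial continued, it followed Section 2.7 and departed from Section 10.1. Section 9.2 has the monitoring committee audit conduct against the protocol, which cannot be done cleanly against two rules. Section 6 places analysis and posting of results in the future, so the error rates quoted with the result still have to be settled.

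**Conclusion.** The concern holds. The two sections give incompatible Stage 1 futility rules, and the operating characteristics claimed in Section 10.1 are wrong for the rule written there: power is 57%, about 33 percentage points below the stated 90%, and the type I error is 2.3% rather than 10%. The stated figures are those of the 5 of 11 rule, which makes 5 the probable intention, though only the sponsor can confirm it.

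The defect is confined to the Stage 1 decision. The final threshold of 11 of 20 is consistent, and the type I error stays within 0.10 either way.

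The figures assume independent patients with a common response rate, all evaluable for the Day 28 endpoint, and a futility rule applied as written. Whether the discrepancy affected the actual trial cannot be judged from the document.

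**What to change.** 1. **Disclose first.** In the study report and the results posting, give the number of responders among the first 11 patients and the cut-off applied. If the count was 6 or 7, say so plainly and state which section the decision followed.
2. **Correct Section 10.1.** Change the Stage 1 rule to stopping at r1 = 5 or fewer of 11, write the final rule as r = 10 (reject at 11 or more of 20), and give the exact type I error (0.099) and power (0.902). Separate symbols remove the double use of r.
3. **If 7 was intended,** change Section 2.7 to match and restate the type I error as 2.3% and power as 57%.
4. **Document the change.** Submit it as a protocol modification under Section 9.1, with a dated explanation that it reconciles two existing passages, so that it is not taken for a boundary chosen after the data were seen.

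The cost is a short text correction, one modification submission and one reported count. No further patients or data collection are needed.

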5. ADVERSE EVENTS AND REPORTING PROCEDURES

5.1 Adverse Events

Hematopoietic cell transplantation (HCT) is an aggressive therapy for the treatment of a number of life threatening disorders, including cancer. In this setting, a very large number of Grade 1, 2 and 3 adverse events (AEs) are expected to occur, regardless of whether or not a patient is participating in a research study. In order to minimize the “background noise” and to focus on clinically significant, meaningful adverse events useful in the assessment of proposed trial the following AE reporting schema is proposed. This schema is intended to capture all AEs that are clinically significant and/or impactful, but minimize “not informative” AE collection.

- Grade 4 and higher AEs will be collected and documented with causality attribution on an adverse event log (AE log), and all AEs meeting the criteria of “serious” as defined at 21CFR§312.32(a), including any that are otherwise Grade 1, 2 or 3 will be collected; identified as serious; and documented on an AE log, including causality attribution.
 - An adverse event is considered serious if it fulfills one of the following criteria per 21CFR§312.32(a):
 - Results in death.
 - Life threatening (patient at risk of death at the time of the event).
 - Requiring new inpatient hospitalization or prolongation of existing hospitalization.
 - Resulting in persistent or significant disability.
 - Other medical events that may not be immediately life threatening or result in death or hospitalization by may jeopardize the patient or require intervention to prevent one of the outcomes listed above
- Laboratory values without a clinical consequence or outcome will not be tracked as adverse events, unless deemed serious.
- Grade 1-3 AEs not meeting these criteria will not be collected, except as follows. Grade 1 to 3 AEs resulting in subject termination or withdrawal from the study will be collected.

All Serious Adverse Events (SAEs) will be tracked until resolution or at least 60 days after the study treatment.5.2 Adverse Event Reporting

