8.1 Primary and Secondary Outcome measures

The primary outcome is to determine the proportion of patients with full dose donor chimerism (FDC) at Day 28 following TLI/ATG/TBI conditioning. FDC is defined as achieving $\geq 95\%$ donor type in the CD3+ lineage within 28 days of donor cell infusion.

The secondary outcome measures include time-to-disease progression assessed at 1 year after hematopoietic cell transplantation (HCT); overall survival (OS) at 1 year; and event-free survival (EFS) at 1 year; and non-relapse mortality at 1 year. The incidence of acute and chronic GVHD following the infusion of allogeneic CD8+ memory T-cells will be assessed at 1 year after HCT.

Recipients will be monitored for HCT toxicities and the rates of GVHD as per the study calendar. STR analysis will be performed on Day 28 +/- 7 days and per the study calendar thereafter. The level of tumor burden will be evaluated at 3 months after transplant and at 6 and 12 months as clinically indicated by standard imaging and blood evaluation procedures specific for the patient disease (refer to Appendix B).

Beyond 12 months and per regular medical care for HSC transplant patients, all recipients will be followed long-term and tracked via the Stanford BMT patient database for overall survival; event-free survival; and late complications such as but not limited to relapse; late chronic GVHD; and infections.

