9.3 Data Management Plan

The Protocol Director, or his designee, will prepare and maintain adequate and accurate participant case histories with observations and data pertinent to the study. The Stanford BMT data monitoring team along with the study coordinator will collect the information required in the Study calendar of events and maintain records for data analysis. The data will be reviewed by the study PI for accuracy against source document data.

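### Section 10.1 evaluates new Grade 3–4 toxicity for 90 days, but Section 5.1 keeps most Grade 3 events off the adverse event log, so a rate taken from that log can only equal or understate it

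*Combined protocol and SAP*

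**What the plan says.** **The evaluation.** Section 10.1 states: "Patients will be evaluated for toxicities, defined as new Grade 3 to 4 toxicities", by CTCAE v5, together with Grade 3 to 4 GVHD by Appendix A. The window is the 90 days after transplant.

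**The collection rule.** Section 5.1 sets the contents of the log:

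- "Grade 4 and higher AEs will be collected and documented with causality attribution on an adverse event log", plus every event that meets the regulatory definition of serious, whatever its grade.
- "Grade 1-3 AEs not meeting these criteria will not be collected, except as follows".
- The exception that follows: "Grade 1 to 3 AEs resulting in subject termination or withdrawal from the study will be collected".
- "Laboratory values without a clinical consequence or outcome will not be tracked as adverse events, unless deemed serious". No grade limit is attached to this exclusion.

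The section gives its reason: in this setting "a very large number of Grade 1, 2 and 3 adverse events (AEs) are expected to occur", and the restriction is meant to reduce noise.

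**Other relevant text.** Section 8.1 says: "Recipients will be monitored for HCT toxicities and the rates of GVHD as per the study calendar". Section 9.3 has staff "collect the information required in the Study calendar of events and maintain records for data analysis". The calendar in Section 7 schedules history, examination, vital signs, performance status, blood counts and chemistry at Days 0, 28, 56 and 90. Its only adverse event row is a weekly SAE evaluation from Day 0 to Day 90. Section 6 says the trial has no data beyond the BMT database, without describing that database's adverse event fields.

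**The concern.** The grade range named in Section 10.1 has two levels, and Section 5.1 leaves the lower one uncollected by default. A toxicity evaluation needs recorded events, and the plan does not say where non-serious Grade 3 events would be recorded.

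What is at stake is the tolerability statement. Section 2.7 aims to raise full donor chimerism with no loss of tolerability and no added morbidity, and Section 10.2 expects no extra regimen-related toxicity. The stopping rule counts only Grade 4 GVHD, so the Section 10.1 evaluation is the plan's only stated measure of general regimen toxicity. Any shortfall would favour the hoped-for conclusion, and a single-arm trial has no concurrent control group in which the same shortfall would show.

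**Working it through.** The plan states no toxicity rate, threshold or power, so there is no figure to reproduce. The check has three steps.

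**1. Which events reach the log**

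| Event within 90 days of transplant | In the Section 10.1 definition | On the Section 5.1 log |
|---|---|---|
| New Grade 4 AE, clinical | Yes | Yes |
| New Grade 3 AE, serious | Yes | Yes |
| New Grade 3 AE, not serious, ends participation | Yes | Yes |
| New Grade 3 AE, not serious, participation continues | Yes | **No** |
| Grade 3–4 laboratory value, no clinical consequence, not serious | Not excluded | **No** |

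**2. Whether another section fills the gap**

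- Section 5.2 concerns SAEs and sends the AEs collected to the same log.
- Section 8.1 refers toxicity monitoring to the calendar. The calendar visits yield clinical data, but its only AE row is for SAEs, and nothing calls for grading or recording non-serious Grade 3 events from those visits.
- Section 9.3 collects what the calendar requires and nothing further.
- Section 6 points to the BMT database. It may hold graded Grade 3 events, but the documents do not say so.

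**3. Direction and size**

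Let n be the number of patients, T the number with at least one CTCAE event meeting Section 10.1, and k the number of those T whose only qualifying events are not on the log, with 0 ≤ k ≤ T.

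- Rate as defined = T/n
- Rate from the log = (T − k)/n
- Shortfall = k/n ≥ 0

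Logged patients are a subset of T over the same denominator, so the direction is fixed. This requires the log to be filtered to new Grade 3–4 events in the 90-day window. It also holds Grade 5 events, serious Grade 1–2 events and SAEs from conditioning, which must be left out of the count.

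Inputs: n = 20 from Section 10.3. Section 6 says enrolment is complete but gives no count, so n = 11 (stage 1 alone, Sections 2.7 and 10.1) is shown as the other possibility. The values of k are assumptions.

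| Assumed k | Shortfall, n = 20 | Shortfall, n = 11 |
|---|---|---|
| 0 | 0 points | 0 points |
| 1 | 1/20 = 5 points | 1/11 = 9.1 points |
| 2 | 2/20 = 10 points | 2/11 = 18.2 points |
| 3 | 3/20 = 15 points | 3/11 = 27.3 points |

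The table stops at 3 for illustration only; k is bounded by T. For example, if T were 16 of 20 (80%) and a quarter of those patients had only unlogged events (k = 4), the log would give 12/20 = 60%, a shortfall of 20 points. Both inputs to that example are assumed.

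**The case against.** The strongest reply is that no planned analysis is shown to be biased. Section 10.1 speaks of evaluating patients and sets no rate, threshold or comparison. Section 8.1 lists no CTCAE rate among the outcomes, and no section names the AE log as the source. Evaluating toxicity and logging reportable events could be separate activities, with calendar data or the BMT database supplying the Grade 3 events. The restriction is also deliberate, and the seriousness criteria are broad enough (hospitalization, or need for intervention to prevent a serious outcome) to catch many Grade 3 events of clinical weight.

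Much of this limits the consequences. The measure is descriptive, the breadth of the seriousness criteria could make k small or zero, and the database may hold what is needed. The direction claim does depend on filtering the log; an unfiltered count could exceed the defined rate. It is also fair that narrowing a definition after accrual has closed is unattractive, because it brings in Grade 5 and serious Grade 1–2 events and so changes what is measured.

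The mismatch itself remains. Section 5.1 says the events are not collected, which is stronger than saying they are not reported, and no section provides another record of them. Reducing noise is a reasonable aim, but Section 10.1 should then promise only what that choice can deliver.

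**Conclusion.** The concern holds. Section 5.1, as written, does not supply the events that Section 10.1 defines, and no other section is shown to supply them. A Grade 3–4 CTCAE rate from the log can equal or understate the defined rate, by 5 points per affected patient at n = 20, or 9.1 points if only 11 were enrolled. The mismatch and its direction are certain once the log is filtered as described. The total size is not: it rests on an assumed k, which may be zero, although the protocol's own expectation about Grade 1 to 3 events makes some unlogged Grade 3 events plausible.

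The effect is confined to the descriptive tolerability result. The chimerism test, the Grade 4 GVHD stopping rule, the GVHD outcomes and the capture of deaths do not depend on it. The point should be corrected before safety results are reported.

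**What to change.** **Option 1: restate the measure.** In Section 10.1, replace the CTCAE definition with what Section 5.1 collects: *AEs of Grade 4 or higher, SAEs of any grade, and Grade 1–3 AEs that end participation, within 90 days after transplant, leaving out laboratory values with no clinical consequence unless serious.* Label the table accordingly, since this is not a Grade 3–4 rate. Report Grade 3–4 acute GVHD separately by Appendix A, and make no claim about overall Grade 3–4 toxicity. The cost is wording only, and the price is a narrower safety statement.

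**Option 2: keep the Section 10.1 definition.** Do this only if the BMT database or the enrolled patients' existing records are confirmed to supply graded Grade 3 events through Day 90. Name that source in the plan and state whether laboratory values count. The cost is a database check and, if needed, chart abstraction in a planned 20 patients, with retrospective grading limited by what was charted.

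Accrual is closed according to Section 6, so neither option alters enrolment or treatment.
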